3.0 Intervention to be studied

This is a multi-site, randomized controlled trial of adult patients (N = 200) hospitalized with severe bacterial or viral infections (complications of HCV, HIV) related to opioid use disorder (OUD). They will be recruited upon diagnosis of their infection and randomized 1:1 to one of two models of care: 1) Infectious Disease management of OUD with Long-Acting injectable buprenorphine (ID/LAB), vs. 2) Treatment as Usual (TAU). ID/LAB is the new model in which OUD is managed by Infectious Disease (ID) specialists and/or Hospitalists concurrent with management of the infectious diseases, using long-acting injectable buprenorphine (LAB). TAU is designed to systematize what is the current practice at the participating hospitals and in most U.S. hospitals while offering a minimum standard of care. TAU will constitute recommendation for MOUD initiation and consultation for addiction medicine when available; in practice, it is typically detoxification from opioids and referral to community-based addiction treatment after hospital discharge. Both models have as their goal stabilization of the OUD and establishing the patient in effective community-based medication maintenance treatment (buprenorphine maintenance or methadone maintenance) for the long term. The primary outcome measure will be the proportion of patients enrolled in effective medication treatment for OUD (buprenorphine, methadone, or extended-release naltrexone) at 3 months (12 weeks) after randomization. Study sites will be three hospitals serving geographically diverse, mixed urban and rural communities across the Eastern U.S.

Randomization: The randomization scheme will be designed by the study statistician and programmed into the data management system. Participants will be randomized to one of the two study arms (ID/LAB vs TAU) using blocks of 4, stratified by Study Site. As soon as a consenting patient has been determined to be eligible, a member of the study team will enter the data system, register the participant, obtain a unique study ID number, and the randomized group assignment will be generated by the system (ID/LAB or TAU). Treatment under the assigned study arm will then begin.

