5.0 Inclusion and Exclusion Criteria/ Study Population

Inclusion Criteria: 1. Adult volunteers over the age of 18 who are able to provide written informed consent in English or Spanish; 2. Current hospitalization with a suspected, or known bacterial or viral (HIV/HCV/HBV) infection including but not limited to bacteremia, Candidal fungemia, osteomyelitis, endophthalmitis, septic thrombophlebitis, infected pseudoaneurysm, community acquired pneumonia, endocarditis, skin/soft tissue infection (SSTI), or septic arthritis; 3. Current moderate-to-severe OUD (DSM-5); 4. Willing to accept assignment to either ID/LAB or TAU, and to participate in research follow-up visits. Exclusions: 1. Severe medical or psychiatric disability making participation unsafe (e.g. imminent suicide risk); 2. Pregnancy, planning conception, or breast-feeding for female participants; 3. Allergy, hypersensitivity or medical contraindication to buprenorphine; 4. Moderate-severe liver impairment in the judgment of the study investigator; 5. Preexisting enrollment on methadone or buprenorphine (SL-B) maintenance AND intending to remain on methadone or buprenorphine maintenance upon discharge (patients already under effective treatment for OUD do not represent the target population of untreated OUD patients entering hospitals, nor would we want to disrupt established effective treatment). 6. Inability or unwillingness of subject to give informed consent.

A screening form that includes chart review and assessment of the above inclusion and exclusion criteria will be used to identify eligibility for the study. This form is located in the appendix.

Eligibility Screening:

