The study team at each Site will conduct regular outreach to the staffs of these services to make them aware of the study and how to refer patients, and work with the attending physician to determine likely eligibility. In many cases, potentially eligible patients will be admitted to the ID or Hospitalist service that is conducting the study. Research assistants will conduct a daily chart review of the patient lists for the Infectious Diseases and Hospitalist teams via the electronic medical record to pre-screen for eligibility. In addition, informational study flyers will be distributed to the Infectious Disease, Addiction Medicine (if applicable) and hospitalist teams with the contact information of the project coordinator for referral of participants or can contact the study team via electronic health record (EPIC) Inbox messaging. Potential participants will be asked if they would like to meet with our study staff. They will be reassured that involvement or non-involvement in the study will not have any bearing on their treatment or hospital stay. All potential participants will be screened in a confidential setting using the computer-assisted interview program.

The Gender and Minority breakdown will vary per study site. These proportions are consistent with the clinical population of opioid users in each region. It is estimated that the sample for our principle recruiting sites will be:

- Hershey, PA: 60% Male, 91% Caucasian, 2% Black or African-American, 4.8% Asian, and 1.4% more than one race; Ethnically 1.5% Hispanic or Latino
- Greenville, SC: 70% Male, 67% Caucasian, 9% Black or African-American, 3% Asian, and 10% more than one Race; Ethnically 7% Hispanic or Latino.
- New Haven, CT: 70% Male, 73% Caucasian, 20% Black or African-American, and 7% Other or More than one Race, Ethnically 27% Hispanic or Latino.

Children will not be included in this study.

6.0 **Number of Subjects**

N = 200 total (N = 100 per study arm), approximately 67 per site-region.

7.0 **Setting**

Patients eligible for the study will typically be admitted either through the emergency department or directly to the medical wards. The study team at each Site will conduct regular outreach to the staffs of these services to make them aware of the study and how to refer patients, and work with the attending physician to determine likely eligibility. In many cases, potentially eligible patients will be admitted to the ID or Hospitalist service that is conducting the study.

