Yale New Haven Hospital sites:

The 944-bed Yale-New Haven Hospital (YNHH), encompassing the York Street and St Raphael campuses in New Haven, CT, serves this medium sized city and its surrounding suburban towns as well as being a tertiary care referral center for the southern New England region. The New Haven hospitals noted above will act as the primary recruiting sites in Connecticut. Bridgeport Hospital, also a member of the YNHH health system, is a 501-bed hospital which serves the southwestern region of the state, and will be a recruiting sub-site, led by [name]. [name] is an internal medicine physician, with addiction medicine experience, sees hospitalized patients and outpatients through the Primary Care Center in Bridgeport. All of these participating hospitals are heavily affected by the opioid epidemic. The Infectious Diseases Section of the Department of Internal Medicine, based at YNHH, is comprised of 36 full-time Faculty, including MPI [name], who will lead the research team there, and 5 others with a Waiver to prescribe buprenorphine. The ID service sees over 200 consultations every month at the York Street and St. Raphael campuses in fiscal year 2017, including 8.5/month MSSA and 14.3/month MRSA bacteremia, often IDU related. The YNHH ID service itself does not have a current standard care for persons with OUD. There is

a newly established Addiction Medicine consult team that is available at YNHH. 'Treatment as usual' ranges from Addiction medicine consultation with possible initiation onto MOUD, to no Addiction consultation followed by detoxification from opioids while inpatient.

St. Mary's Hospital:

Saint Mary's Hospital, owned by Trinity Health of New England is a 347-bed hospital located in Waterbury, Connecticut, in the Naugatuck Valley. This region has been impacted greatly by the opioid epidemic, including associated opioid-related hospitalizations and infections. [name] is an infectious disease specialist with expertise in HIV and HCV disease management and will be the local site investigator. He sees patients both in the hospital and in his outpatient clinic. Current standard care for the OUD for these patients consists of detoxification and referrals for outpatient treatment after hospital discharge.

Columbia and Mid Atlantic site:

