10.0 Study Design / Methods

Design Overview: This is a multi-site, randomized controlled trial in which adult patients (N = 200) hospitalized with known, or suspected, severe bacterial or viral infections (complications of HCV, HIV) and concurrent opioid use disorder (OUD) will be recruited upon admission to hospital and randomized 1:1 to one of two models of care:

1) Infectious Disease management of OUD with Long-Acting injectable buprenorphine (ID/LAB), vs. 2) Treatment as Usual (TAU). ID/LAB is the new model in which OUD is managed by Infectious Disease (ID) specialists and/or Hospitalists concurrent with management of the infectious diseases, using long-acting injectable buprenorphine (LAB). TAU is designed to systematize what is the current practice at the participating hospitals and in most U.S. hospitals while offering a minimum standard of care. TAU will constitute recommendation for MOUD initiation and consultation for addiction medicine when available; in practice, it is typically detoxification from opioids and referral to community-based addiction treatment after hospital discharge. Both models have as their goal stabilization of the OUD and establishing the patient in effective community-based medication maintenance treatment (buprenorphine maintenance or methadone maintenance) for the long term. The primary outcome measure will be the proportion of patients enrolled in effective medication treatment for OUD (buprenorphine, methadone, or extended-release naltrexone) at 3 months (12 weeks) after randomization. Study sites will be three hospitals serving geographically diverse, mixed urban and rural communities across the Eastern U.S.

Randomization: The randomization scheme will be designed by the study statistician and programmed into the data management system. Participants will be randomized to one of the two study arms (ID/LAB vs TAU) using randomly permuted blocks of 4 stratified by Study Site. As soon as a consenting patient has been determined to be eligible, the Study Coordinator at the Site will enter the data system, register the participant, obtain a unique study ID number, and the randomized group assignment will be generated by the system (ID/LAB or TAU). Treatment under the assigned study arm will then begin.

Buprenorphine and LAB initiation:

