Secondary outcomes: 1) Days using opioids, and days injecting drugs per 28 days prior to each major assessment point (weeks 4, 8, 12, and 24 post randomization) (longitudinal, continuous); 2) Urine toxicology-confirmed abstinent (urine toxicology negative for illicit opioids, and self-report negative over past 7 (at week 1) or 30 days (weeks 4, 8, 12, 24) (longitudinal, binary); 3) Completion of the prescribed course of antimicrobial therapy (binary), Re-hospitalization for infection by week 12 (binary); 4) Days using other drugs/alcohol per 28 days prior to each assessment (longitudinal, continuous); 5) Urine toxicology positive for non-opioid drugs (longitudinal, binary); 6) Social functioning and quality of life (WHOQOL-Bref) at 12 and 24 weeks after randomization (longitudinal, continuous); 7) Modified PEG Pain Scale at each assessment (Longitudinal, continuous) 8) HIV risk behaviors—days in past 28 days of vaginal or anal sex without a condom at weeks 4, 8, 12, 24 (longitudinal, continuous); 8) Any needle sharing in past 28 days (longitudinal, binary); 9) Treatment satisfaction (via the TSR)¹² at 12 and 24 weeks (longitudinal, continuous); 10) Discharge “against medical advice” (binary); 11) Cure of index infection (binary); 12) HCV cure or link to treatment (binary); 13) HIV Viral suppression (Viral Load < 200 copies), if HIV positive (binary); 14) overall hospitalization by week 12; 15) ED visits by week 12; 16) Serious adverse events (SAFETEE and non-fatal and fatal overdose) (binary).

Additional variables: *Covariates, primary and secondary analyses: Stratification factors:* Site (3 sites: YNHH; Columbia/Penn State Hershey; South Carolina/Greenville) will be included as a fixed effect in all analyses. *Covariates:* In general, the baseline score for each outcome measure (where applicable) will be included as a covariate in outcome analyses. *Moderators:* A range of baseline moderator variables will be explored including 1) Demographic characteristics (gender, age, ethnicity, living situation (domiciled vs homeless); 2) Modified Pain PEG scores at baseline (continuous) 3) Evidence of fentanyl use at admission (urine toxicology, self-report) (binary); 4) Other substance use at baseline (any cannabis, any stimulant, any heavy drinking days; binary); 5) Probable major depression at baseline (binary based on PHQ score); 5) Type of infection (endocarditis/ osteomyelitis/bacteremia/ cellulitis/ etc.). *Mediators:* 1) Social functioning

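### A single block size of 4, printed in the protocol and stratified only by site, means unblinded site staff who track assignments could deduce up to one in three in advance

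*Combined protocol and SAP*

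**What the plan says.** Section 3.0 (Randomization) assigns participants "using blocks of 4, stratified by Study Site", and section 10.0 (Randomization) repeats this as "using randomly permuted blocks of 4 stratified by Study Site". Section 10.0 also says that patients are "randomized 1:1 to one of two models of care", so each block holds two ID/LAB and two TAU assignments. Neither section mentions a second block size or withholding the size from sites.

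Section 12.0 defines the stratification factor as "Site (3 sites: YNHH; Columbia/Penn State Hershey; South Carolina/Greenville". Section 6.0 gives the size as "N = 200 total (N = 100 per study arm), approximately 67 per site-region". Section 7.0 describes several Connecticut hospitals, including one that "will be a recruiting sub-site".

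On procedure, section 10.0 says that once a consenting patient is found eligible, "the Study Coordinator at the Site will enter the data system, register the participant" and the system returns the arm. The research Nurse Care Manager gives the ID/LAB injection and also works with TAU participants on a similar schedule (section 10.0). Site coordinators can access their own site's data (section 12.0).

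**The concern.** Central generation of the assignment protects the list from being read. It does not protect against working out the next entry from the entries already used, and a short, constant, published block makes that easy when past assignments are visible.

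The deduction would be made before the next patient is approached, and that is where the discretion lies. Staff choose whom to approach from a daily chart review (sections 5.0 and 8.0) and lead the consent discussion (section 9.0). Some exclusions are matters of judgement, such as "Severe medical or psychiatric disability making participation unsafe" and the investigator's view of liver impairment (section 5.0). Another exclusion turns on whether a patient already on maintenance intends to stay on it, which bears directly on the primary outcome.

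No bad faith is needed. Section 10.0 expects the first injection typically on day 3, requires a period of negative blood cultures first, and concedes that injection before discharge is not always feasible. Staff who believe ID/LAB is next have a practical reason to prefer a patient who will stay. If such choices track prognosis, the arms differ at baseline, and the intention-to-treat comparison of 12-week enrolment inherits the difference.

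**Working it through.** **The plan's own figure.** The documents give no figure for predictability. The nearest stated figure is the sample size in section 12.0: 40% versus 59.7%, two-sided 5%, 80% power. With the pooled-variance formula and no continuity correction, n = [1.960·√(2 × 0.4985 × 0.5015) + 0.842·√(0.40 × 0.60 + 0.597 × 0.403)]² / 0.197² ≈ 99.9, so 100 per arm; power at 100 per arm is 80.03%. N = 200 is reproduced and is not affected by this point.

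**Inputs from the documents.** Block size 4, allocation 1:1, three site strata, about 67 patients per site.

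**Certain assignments.** A 2:2 block has 6 equally likely orders. An assignment is certain once one arm's two places are used.
- In AABB and BBAA, positions 3 and 4 are certain: 2 orders × 2 = 4.
- In the other 4 orders, only position 4 is certain: 4 × 1 = 4.
- Total: 8 of 24 positions, or 1/3. By position, the chance of certainty is 0, 0, 1/3, 1.

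**At the planned size.** 67 patients make 16 full blocks plus 3: 16 × 4/3 + 1/3 = 21.67. 66 patients make 16 full blocks plus 2: 21.33. Over 67 + 67 + 66, the total is 64.7 of 200, or 32.3%.

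**Best guess.** Always guessing the arm with more places left is right in 17 of 24 positions, 70.8% (70.4% in simulation at 67 per site). Simple randomization gives 50%.

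**Effect on the primary comparison.** This step rests on assumed behaviour. Suppose staff raise success probability by d on every slot known to be ID/LAB and lower it by d on every slot known to be TAU. One third of each arm is affected, so bias = d/3 + d/3 = 2d/3. With a true rate of 40% in both arms, SE = √(2 × 0.4 × 0.6 / 100) = 0.069. Type I error is the chance that a normal variate shifted by bias/SE falls outside ±1.96.

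| Assumed steering on certain slots | Bias (points) | Type I error |
|---|---|---|
| 5 points, one certain slot in four | 0.8 | 5.2% |
| 2 points, every certain slot | 1.3 | 5.4% |
| 5 points, every certain slot | 3.3 | 7.7% |
| 10 points, every certain slot | 6.7 | 16% |

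The table uses complete blocks. At 32.3% certain, the 5-point row gives 3.2 points and about 7.5%.

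**With varying block sizes.** Simulated at 67 per site, against a guesser who knows the set of sizes but not their order:

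| Block sizes | Certain | Best guess correct |
|---|---|---|
| 4 only | 32% | 70% |
| 4, 6 | 5.5% | 69% |
| 4, 6, 8 | about 2% | 68% |

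With 4/6/8, the 5-point scenario on certain slots gives a bias of about 2 × 5 × 0.022 = 0.2 points and type I error of about 5.0%. A longer fixed block does much less: 25% remain certain at size 6 and 20% at size 8.

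**The case against.** The strongest reply is that predictability is not bias. To know the next assignment, staff must follow every earlier one in the stratum, in order. The documents spread the work: research assistants pre-screen, a physician, research assistant or nurse coordinator consents, and the coordinator registers. If the Connecticut hospitals in section 7.0 share one stratum, as the three-site list suggests, staff at one hospital do not automatically see assignments at the others. Many screening items are objective or instrument-based (age, language, the opioid dependence screen, the pregnancy test). Covariates associated with outcome will be adjusted for. The steering sizes have no source in the documents, and the direction could be reversed: staff might steer the sickest patients toward the injection and so bias against ID/LAB.

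Most of this stands, and it limits the claim. One in three is a ceiling on what could be deduced. A reader might infer that staff do know a third of assignments, or that one small team sees them all; the documents say neither. Covariate adjustment is partial protection, since it cannot reach unmeasured motivation or stability. What does not stand is the suggestion that system generation settles the matter: coordinators can see their own site's data, the arms are visible, and the discretion comes before registration.

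The remedy also has a limit. If staff acted on every guess, not only on certainties, 5 points of steering would give 4.2 points of bias and 9.2% type I error with complete blocks of 4 (4.1 points and 9.1% at 67 per site). With 4/6/8 this would still be about 3.6 points and 8%. A reader might take the larger figures as the harm that varying blocks would prevent; they are not.

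**Conclusion.** The point holds as an avoidable weakness in allocation concealment. What is certain is the predictability: 1/3 of positions in complete blocks, about 32% at the planned site sizes, available to anyone who tracks the stratum, and harder to exploit in Connecticut. That the trial is unblinded is inferred from the design. The protocol does not label it open-label, and the reference to blinding information in section 18.0 belongs to a generic list of pharmacy services.

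Selection bias is a possibility whose size and direction depend on behaviour that the documents do not describe. Consistent 5-point steering toward ID/LAB on every certain slot gives 3.3 points of bias and 7.7% type I error; weaker or occasional steering gives little. A reader might conclude that the primary comparison is already biased. Nothing in the documents shows that. The case for change is that the remedy is cheap and removes nearly all of the certain assignments.

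**What to change.** In sections 3.0 and 10.0, replace 'blocks of 4' with 'randomly permuted blocks of randomly varying size, not disclosed to sites'. Use sizes such as 4, 6 and 8, recorded only with the study statistician and in the data system. Section 10.0 refers to current participants already past discharge, so enrolment appears to be under way; in that case apply the change to all remaining assignments. It cannot alter those already made.

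The cost is one reprogrammed randomization list and a short multi-site amendment with IRB review. The statistical downside is a possible end-of-list imbalance of up to 4 patients per site instead of 2. The amendment should not claim to remove all predictability, because probabilistic guessing is hardly affected.

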Demographics, Drug Use and Treatment History: This brief assessment records basic demographics such as race/ethnicity, gender, housing status (homeless vs domiciled; whether living with other drug users), insurance, employment, income, marital status, and children. It will also include drug use and treatment history such as age at onset and current use of opioids and other drugs/alcohol, history of overdose, history of substance related hospitalization, and past episodes of treatment for SUD.

Locator Form: The locator form will collect patient related information not covered in the Demographics form such as social security number and contact information of family and/or close friends. Contact information will be used if primary methods of communication such as primary phone number are unsuccessful.

Opioid and Other Substance Use

- Withdrawal symptoms: The Clinical Opiate Withdrawal Scale (COWS) is an 11-item scale used in both inpatient and outpatient settings to reproducibly rate common signs and symptoms of opiate withdrawal and monitor these symptoms over time.
- Timeline Follow-Back (TLFB)^{27,28}(15 mins) assesses self-reported alcohol and other drug use including opioid use route of use and form of drug, for the 30 days before baseline, and for each day over the follow up period, using calendars and memory aids to enhance recall. The TLFB has good psychometric properties, including test-retest reliability with multiple populations, and content, criterion, and construct validity across multiple related measures.¹¹⁸
- Mini-International Neuropsychiatric Interview²⁹ (MINI) DSM V version 7.0.2- for OUD diagnosis and other SUD diagnoses and DSM V psychiatric disorders.
- Opioid Craving: Two additional questions will assess intensity and number of days of opioid craving using a 10-point Likert scale.
- Alcohol Use Disorder Identification Test³⁰ (AUDIT; 10 mins) assesses for presence and severity of alcohol use disorder

Mental Health

- MINI DSM V version 7.0.2 (see above)
- Patient Health Questionnaire (PHQ-9)^{31,32}(5 mins) was developed for use in primary health settings and screens for DSM psychiatric diagnosis of major depression and generalized anxiety at baseline.
- PTSD Check List-5 (PCL5) for PTSD³³ (2 mins), is a 5 question assessment that evaluates for presence and severity of PTSD symptoms.

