- Adult ADHD Self Report Scale (ASRS) for ADHD symptoms³⁴ (4 mins) is an 18 question assessment for presence and severity of ADHD symptoms by self-report.

Quality of Life: WHOQOL-Bref³⁵ (5 mins) is a well validated and widely used scale for persons with substance use disorders that measures the quality of social and occupational functioning as well as other domains.

Medical/Infectious Disease Questionnaire: This form documents the completion of antimicrobial therapy and re-hospitalization for infection. The initial evaluation documents the relevant infection and medical details such as infection site, organism, and stage. It also extracts the type of anti-infective, route of administration, dose, planned duration and, at select sites, knowledge of, experience with, and attitudes related to HIV Pre-Exposure Prophylaxis (PrEP). Information collected on follow-up will be alteration of treatment plan, infection related adverse events (e.g. PICC complications, drug reaction/toxicity to anti-infective agent prescribed by non-study clinicians, etc), intervening hospitalizations, and questions related to PrEP. Current study participants, at select sites, who are beyond the hospital-discharge timepoint will be asked these PrEP questions retrospectively, at one timepoint, at the next scheduled study follow-up visit.

Severity Scoring: The Elixhauser Comorbidity Index³⁶ is a validated scoring index for predicting mortality based on patient comorbidity. This will be performed via chart review.

Substance Use Treatment (SUTx) Form: This questionnaire documents the details of MOUD and substance use treatment history in the intervention and TAU arms. For those participants receiving LAB, it documents date of administration, dose, location and prescribing provider. The TAU section of the questionnaire queries the variety of different forms a substance use treatment that participants may or may not receive in the community. This includes MOUD (buprenorphine, extended-release naltrexone, or methadone) prescribed by non-study related physicians, behavioral therapy (i.e. 12 step

programs), and whether participants have enrolled in a community opioid treatment program (OTP).

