12.0 Data Management

Power Analysis: Previous studies of buprenorphine initiation in an Emergency Department⁴² and on a medical inpatient service,⁴³ yielded rates of post-discharge buprenorphine maintenance treatment in the 70% range. The Emergency Department study implemented a Screening, Brief Intervention and Referral control condition, similar to the TAU condition planned in the current protocol, which yielded a rate of post-discharge buprenorphine maintenance treatment of 45%. We anticipate that the population recruited for this study will be among the most severely ill patients with OUD, being those requiring hospitalization for infections, and therefore we conservatively assume that the proportion of patients meeting our primary outcome (enrolled in MOUD 12 weeks after hospital discharge) will be 40% in the TAU arm and 60% in ID/LAB arm. We have chosen a sample size of N = 200 total (N = 100 per study arm), in order to ensure sufficient power (power = 80%) with a two-sided level of significance of 5% to detect a difference of at least 19.7% between the TAU and ID/LAB treatment groups (i.e., 40% treatment enrollment in the TAU arm and at least 59.7% treatment enrollment in the ID/LAB arm). This rate difference of 19.7% is equivalent to an odds-ratio of 2.2 and would be clinically meaningful.

Data Analysis Plan:

Primary outcome: The primary outcome will be a binary indicator of whether a patient is enrolled in and receiving effective MOUD (buprenorphine, methadone, or injection naltrexone) at 12 weeks (3 months) after randomization.

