Secondary outcomes: Statistical Models: For each of the secondary outcomes (see above) the effect of randomization to the ID/LAB arm compared to the TAU arm will be estimated with a model of the same general form as for the primary outcome (independent variables: treatment assignment (ID/LAB vs TAU), Site as a fixed effect, and baseline score as covariate where relevant) using logistic regression models (for binary outcomes), generalized linear model (for continuous outcomes), or longitudinal generalized mixed effects model (for longitudinal outcomes) with appropriate link functions (e.g. logit for binary outcomes). Longitudinal outcomes analyzed using a mixed effects models will utilize a generalized estimating equation with an autoregressive correlation structure (AR(1)) to account for within subject correlation over time, as well a random intercept accounting for between subject variability. In addition to site, covariates that are found to be related to the outcomes will be added to the models to improve the power for detecting significant differences.

Moderation and Mediation: Moderation Statistical Models: The effect of randomization to the ID/LAB vs TAU arms will be estimated for subpopulations based on the demographic and baseline characteristics selected as moderators (see above). We will estimate the moderation effect on primary outcome using a similar model to Aim 1 primary outcome with the inclusion of moderator by treatment interaction: $Y_i = \beta_0 + \beta_1 Trx_i + \beta_2 M_i + \beta_3 Trx_i M_i + \beta_4 C_i + s_i$ where M_i is the moderator status for i^{th} subject and Trx_i is subject's treatment assignment. Regardless of the significance of the interaction term, we will use the model to estimate the 95% confidence interval of the treatment effect for each level or category of the moderator variable, or the treatment effect at selected values of the moderator variable, if continuous. The moderator analyses are exploratory and hypothesis generating, but significant moderator effects can be useful in planning future efforts at implementation of medication treatment for opioid use disorder in medical settings by identifying subgroups that may particularly benefit. Identifying subgroups where there is less benefit may suggest future modifications to the implementation strategy to achieve better effect in those subgroups.

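### The baseline Elixhauser score and the history of substance-related hospitalization are collected but pre-specified in no analysis, so they can reach the hospitalization, ED, cure and SAE models only through an undefined, outcome-driven covariate rule

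*Combined protocol and SAP*

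**What the plan says.** **Collection.** The study schedule places the Elixhauser index at baseline only. Section 10.0, under Severity Scoring, says that it "is a validated scoring index for predicting mortality based on patient comorbidity. This will be performed via chart review". Section 8.0 puts the baseline assessments before randomization. The demographics and drug-use assessment in Section 10.0 includes "history of substance related hospitalization".

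**Analysis.** Section 12.0, Additional variables, fixes site in every model and adds: "In general, the baseline score for each outcome measure (where applicable) will be included as a covariate in outcome analyses". The moderators listed there are demographics, pain, fentanyl use, other substance use, probable depression and type of infection. The mediators are social functioning, craving and pain. Neither the Elixhauser score nor hospitalization history appears in these lists or in the model descriptions that follow.

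For secondary outcomes, Section 12.0 gives a model of the same general form as the primary one. In parentheses it names the terms: treatment, "Site as a fixed effect, and baseline score as covariate where relevant".

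**Data-driven additions.** Two further statements in Section 12.0 allow other covariates. The paragraph on significance testing says covariates will be examined for association with outcome and adjusted for if associated. The paragraph on secondary models says covariates found to be related to the outcome will be added to gain power. Neither gives a list of candidates, a threshold or a selection procedure.

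**The concern.** Re-hospitalization and ED presentations belong to Aim 3, and serious adverse events carry the safety comparison. Eligibility in Section 5.0 runs from skin and soft tissue infection to endocarditis and candidal fungemia, so illness at entry should vary widely. Randomization is stratified by site alone, so nothing in the design balances severity between arms.

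The trial collects a pre-randomization severity score and states no use for it. For these outcomes there is no earlier value of the same measure to adjust for. The usual device of adjusting for baseline therefore does nothing, and whether severity enters is decided after the outcome has been seen. Two analysts following the plan could fit different models to the same outcome and report different odds ratios. Omitting a truly prognostic covariate also costs some power and leaves the estimate exposed to a chance difference in illness between arms.

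**Working it through.** **1. The plan's own figure.** The primary outcome is sized at "40% treatment enrollment in the TAU arm and at least 59.7% treatment enrollment in the ID/LAB arm", two-sided 5%, 80% power. With pooled variance and no continuity correction:

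n per arm = [1.960·√(2·0.4985·0.5015) + 0.842·√(0.40·0.60 + 0.597·0.403)]² / 0.197² = (1.386 + 0.583)² / 0.0388 ≈ 100.

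Power at 100 per arm is 80.0%, and the odds ratio is (0.597/0.403)/(0.40/0.60) = 2.22. The stated design reproduces. It uses no covariates, so nothing below changes it.

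**2. Which terms are named for each outcome** (Section 12.0)

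| Outcome | Baseline score defined? | Explicitly named terms |
|---|---|---|
| Infection re-hospitalization | No | treatment, site |
| Overall hospitalization | No | treatment, site |
| ED visits | No | treatment, site |
| Cure of index infection | No | treatment, site |
| Serious adverse events | No | treatment, site |

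**3. Effect on power.** The documents give no event rates for these outcomes and no prognostic strength for the score, so both are assumed. Each outcome is taken as yes/no with events of 40% and 22%, 100 per arm and three sites. The covariate is one standardized normal variable. The model is logistic, with a Wald test of treatment and 4,000 simulated trials per row. Marginal event rates are held fixed as the covariate effect varies.

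| Odds ratio per SD (assumed) | Power, treatment + site | Power, with covariate | Gain (points) |
|---|---|---|---|
| 1.0 | 80.2% | 80.2% | about 0 |
| 1.25 | 78.6% | 79.1% | 0.5 |
| 1.5 | 79.0% | 80.2% | 1.2 |
| 2.0 | 79.2% | 81.9% | 2.7 |
| 3.0 | 77.7% | 85.6% | 7.9 |

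Simulation error per figure is √(0.8·0.2/4000) ≈ 0.6 points.

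**4. Chance imbalance.** The SE of a standardized mean difference is √(1/100 + 1/100) = 0.141 SD, so a 2-SE imbalance is 0.283 SD. The approximate shift in the unadjusted log odds ratio is 0.283 × ln(odds ratio per SD):

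| Odds ratio per SD | Shift in log odds ratio | Factor on odds ratio |
|---|---|---|
| 1.25 | 0.063 | 1.07 |
| 1.5 | 0.115 | 1.12 |
| 2.0 | 0.196 | 1.22 |
| 3.0 | 0.311 | 1.36 |

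For scale, at 40% and 22% the SE of the unadjusted log odds ratio is √(1/40 + 1/60 + 1/22 + 1/78) = 0.316. The 95% half-width is 1.96 × 0.316 = 0.62. At an odds ratio per SD of 2, this rather extreme imbalance moves the estimate by about a third of that half-width.

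**5. Sparse events.** At 40% and 22% there are 62 expected events. With treatment, two site terms and Elixhauser that is 62/4 ≈ 15 events per coefficient; adding history gives 62/5 ≈ 12. If only 10% of participants had a serious adverse event (an assumption), 20 events would give 20/4 = 5 and 20/5 = 4. A second forced covariate is therefore not safe everywhere.

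**The case against.** The best defence is that the plan does provide for adjustment. Both data-driven statements are open to any covariate, so if the Elixhauser score predicts hospitalization it may be added, and if it does not, little is lost. That stands against a reading one might be tempted to make, that the two variables enter no analysis and the models run without them. The text does not support that reading. What the defence leaves untouched is that entry turns on an unstated criterion applied after outcomes are known.

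Second, the primary model takes in the listed covariates and moderators, and the secondary models share its general form. On a broad reading, type of infection and the other moderators would be in them too. The parenthesis for secondary models points the narrower way, so the text is ambiguous. It would be too strong to say that these models certainly lack any prognostic term. On either reading, the Elixhauser score and hospitalization history are not named.

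Third, the documents describe the index as validated for mortality. Its relevance to readmission, ED use, cure or adverse events is plausible but assumed. The history item covers substance-related hospitalization only, not prior admissions generally. Nothing shows that the chart-review score will be complete.

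Fourth, randomization protects the unadjusted comparison, and its confidence interval already allows for chance imbalance. This stands in full.

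**Conclusion.** The point holds as a gap in pre-specification. The trial collects a pre-randomization severity score, and the plan leaves its use in five outcome models to an open, outcome-driven rule. Naming the score in advance is the better method.

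The benefit is modest: about 0.5 to 3 power points for an assumed odds ratio per SD from 1.25 to 2, and about 8 at 3. These figures rest on assumed event rates of 40% and 22% and on a single normally distributed covariate. Adding both covariates together was not simulated. The firmer gains are a model fixed before the outcomes are seen and some protection against chance imbalance in illness.

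A reader might infer that the Aim 3 or safety comparisons are biased or invalid. They are not: the unadjusted randomized comparison remains valid, no stated figure is wrong, and N = 200 is unchanged. This is a cheap improvement.

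**What to change.** In Section 12.0, for infection re-hospitalization, overall hospitalization, ED visits, cure of the index infection and serious adverse events:

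- Name the baseline Elixhauser score (continuous) as a fixed covariate beside treatment and site, and state that this replaces outcome-driven selection for these outcomes.
- Add history of substance-related hospitalization (yes/no) only where the event count supports a second covariate, with the minimum count set in advance.
- If serious adverse events are few, keep that model to treatment and site, or use a penalized fit, and say beforehand which applies.
- Say how a missing Elixhauser score will be handled, and note that the adjusted odds ratio is conditional on the score.

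The cost is a few lines of text and one or two degrees of freedom per model. No new data, visits or participants are needed. The change should be made before outcome data by arm are examined.
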